- 3. Assess the effect of lithium treatment of bipolar disorder on 5-H T_{IA} BP. Chronic lithium in animal studies does not affect somatodendritic 5-HT_{1A} B_{max} in the dorsal raphe nucleus but decreases 5-HT_{1A} B_{max} in frontal cortex and hippocampus. We propose to perform baseline 5-HT_{1A} scans with [11C]CUMI-101 or [18F]MeFWAY and repeat scans 6-10 weeks from the time of therapeutic or highest tolerable dose of lithium monotherapy. Our preliminary 5-HT_{1A} data in bipolar subjects suggest that as a group they have slightly higher 5-HT_{1A} BP than controls with a sex by diagnosis interaction. We hypothesize that regardless of sex, 5-HT_{1A} BP will downregulate in response to chronic lithium.
- 4. Assess the effect of lamotrigine treatment of bipolar disorder on 5-HTT and 5-HT₁₄ BP. We estimate based on our experience with bipolar subjects in our clinic that 50% of the subjects will not be eligible for lithium monotherapy. We propose to treat this group with lamotrigine. Lamotrigine, like lithium, alters 5-HT_{1A} B_{max} and also activity. There are no data regarding lamotrigine and its effects on 5-HTT. We propose to explore the effect of lamotrigine on 5-HTT and 5-HT_{1A} in order to determine if this medication also acts via alteration of these proteins. We will determine the relationship between BP change and antidepressant effect.
- 5. Assess the effect of lithium treatment of unipolar depression on 5-HTT BP. We will perform baseline and

Approved: 12/13/2019
Expiration Date: 12/12/2020
Stony Brook University Human Subjects Committee (IRB)
PSF 2/23/15

Page 2 of 37

IRB# 2012-1826-F PI: [name]

post treatment [11C]DASB scans in 10 unipolar depressed subjects. We will determine if the effects of lithium treatment are specific to bipolar depression.

B. Background and Significance

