We will use the radiotracer [11C]DASB to measure serotonin (5-HT) transporter binding and [11C]CUMI-101 to measure serotonin receptors in the brain of depressed or recently depressed bipolar subjects using Positron Emission Tomography (PET) before and after treatment with a mood stabilizer. We propose to assess how the clinical responses to two types of mood stabilizer treatment relate to the state of the serotonin system. The two treatments we intend to compare are lithium and lamotrigine. We propose to perform [11C]CUMI-101 and [11C]DASB in 38 medication free bipolar subjects during a major depressive episode and compare 5-HTT and 5-HT_{1A} binding potential in 38 healthy volunteers. We will also examine the diagnostic specificity of lithium response by studying 10 unipolar depressed subjects in an identical manner.

We will obtain blood samples from all subjects in the protocol in order to be able to evaluate their genetic information. We plan to analyze the DNA from the blood to assess for genome wide and single nucleotide polymorphisms and their associations with MRI and PET brain imaging measures. For example, the effects of the C(-1019)G 5-HT1A promoter polymorphism has been shown to affect the binding of our 5-HT1A tracers in humans. The genetic information may also be used to study the general pathophysiology of major depression, bipolar disorder or past suicidal ideation in the subjects. Blood RNA will also be evaluated because it tells us whether the gene variants are associated with altered gene expression. We expect gene variants with altered expression levels to be of greater pathophysiological consequence.

2. Research Site

Stony Brook University Human Subjects Committee (IRB) PSF 2/23/15

Page 9 of 37

IRB# 2012-1826-F PI: [name]

MRI scans, research interviews, clinical assessments and treatment will take place at Stony Brook University Medical Center. PET scans will take place at the Yale University PET Center in New Haven, CT.

3. Study Sample

86 subjects in total are proposed. The power calculations are below.

Age range: 18-70

Total subjects: N = 86 (38 bipolar, 38 healthy volunteer, 10 unipolar)

Gender: Male and female representation are about equal.

No ethnic/racial/gender group is excluded.

4. Screening

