PET experiments will be conducted at the Yale University PET Center, [name], in New Haven, CT. [11C]CUMI-101 and [11C]DASB scans will be performed. Participants may have only one of these scans, depending on radiotracer availability. The PET scans will preferably be performed after the MRI scan, but the order may be reversed if needed.

Participants will be provided with transportation from Stony Brook University to Yale University by a combination of taxi/car service, ferry, and/or train. Participants will be accompanied by a staff member while traveling to/from Yale University. Participants will arrive the night before the scheduled scan day(s) and be given accommodations at a nearby hotel at no cost to them.

On the day of the scans, a urine pregnancy test will be done on females to ensure that pregnancy has not occurred between the time of the screening and the PET scans. All participants will also have a urine drug screen. The preparation of the subject will include the placement of one venous lines (for radiotracer injection), a second venous line (for and blood sampling), and an arterial line (for blood sampling). An experienced physician will place the arterial line after infiltration of the skin with 1% lidocaine. A transmission scan is then obtained. Before injection of the radiotracer, approximately 8ml of venous blood will be collected. For the [¹¹C]CUMI-101 scan, up to 20 mCi of [¹¹C]CUMI-101 (mass dose of 5 µg or less) will be administered i.v. after the transmission scan. Emission data will be collected for up to 120 minutes. At the time of injection, arterial sampling will be initiated. In order to demonstrate that the arterial and venous metabolites are the same for late time points, a 4 mL venous sample will be initiated at 60 and 90 minutes. 90 ml or less will be collected during scan time.

At the end of the scan, subjects will be provided with a light meal and be allowed to relax. For the [\frac{11}{C}]DASB scan, the subject will go back on the scanner table and an injection of up to 20 mCi of [\frac{11}{C}]DASB, (mass dose of 10 \mug or less) will be administered. Emission scan and arterial sampling will be resumed as described above. A 4 mL venous sample will be initiated at 50 and 80 minutes. Thus, maximal blood sampling during the entire PET procedure will be approximately 180 ml (about 12 tablespoons).

IRB# 2012-1826-F PI: [name] Stony Brook University Human Subjects Committee (IRB) PSF 2/23/15

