We will ask controls if they would be willing to participate in an adult attachment interview. The interview is approximately 45-75 minutes long and can be completed over the phone or in person. The interviews are audio recorded and transcribed. The recorded interviews are kept confidential with a participant number. There are no risks or benefits associated with this optional interview.

Treatment Procedures

Site of Treatment

Patients will be treated on an outpatient basis at Stony Brook University Medical Center. Patients may visit the Clinical Research Center or a LabCorp collection site for sample collection, if needed on rare occasions.

Treatment Choice

At baseline, patients will have a [11C]CUMI-101 and [11C]DASB PET scan. All patients will then receive outpatient pharmacologic treatment with lithium administered as follows: Day 1, 2 and 3, 300 mg bid; Days 4-7 lithium 300 qam and 600 qhs. A blood sample will be drawn (approximately 8.5 ml) to check the lithium level as close to Day 7 as possible. The lithium level will be titrated to a therapeutic plasma level of 0.8-1.2 mEq/l; the lithium level will be checked weekly via a blood sample of approximately 8.5 ml until this level is reached. Patients may have additional blood samples drawn to check the lithium level after reaching this level, if needed. Patients will not undergo lithium monotherapy if they have a documented history of at least two failed trials of lithium of at least 4 weeks duration with therapeutic blood levels for a major depressive episode. If they have not responded to adequate prior lithium treatment while depressed or refuse lithium, they will be given lamotrigine. Lamotrigine will be started at 25 mg bid and increased to 50 mg bid after 2 weeks and again increased to 100 mg bid after an additional 2 weeks.

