After 6-10 weeks from the time of therapeutic or highest tolerable dose of treatment with either agent they will have repeat [\frac{11}{C}]CUMI-101 and [\frac{11}{C}]DASB PET scans. Blood levels of the lithium will be measured at the time of the repeat scan. At 6 weeks, if patients have not shown at least a 50% improvement in their HDRS score from the baseline interview they will be switched to lamotrigine. Similarly, if patients cannot tolerate treatment, they will be switched to lamotrigine and we will repeat both [\frac{11}{C}]CUMI-101 and [\frac{11}{C}]DASB scans 4-10 weeks after subjects are on therapeutic levels of lamotrigine. If subjects cannot tolerate either treatment, or if the subject scores a CGI-I (severity of illness) score of 4 ("moderately ill") or more after the week 4 visit for two visits in a row, and/or a CGI-II (global improvement) score of 6 ("much worse") or 7 ("very much worse") for 2 visits in a row, the subject will be considered a non-responder and will receive the repeat [\frac{11}{C}]CUMI-101 and [\frac{11}{C}]DASB scans. They will then receive open treatment in our clinic.

IRB# 2012-1826-F PI: [name] Stony Brook University Human Subjects Committee (IRB) PSF 2/23/15

PSF 2/23/15 Page 21 of 37

Neither lithium nor lamotrigine is approved by the FDA for acute treatment of depressive episodes in patients with bipolar disorder, and neither drug is approved for treatment of unipolar depression. Thus, the use of both drugs as treatment for depression in this study is off-label. Nevertheless, both drugs represent reasonable treatment options for depression which has failed to respond to traditional antidepressants in either bipolar or unipolar depressive disorders. There have been several reports of the efficacy of lithium and lamotrigine in both bipolar and unipolar depression (175-178). In this study, unipolar depressed patients will only be treated with lithium.

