To assess the impact of lithium on the neuroreceptor measures we conservatively use the higher test/retest variability of the [¹¹C]DASB compound and assume a 20-25% change in both 5-HT_{1A} and 5-HTT after chronic lithium based on preclinical data. ¹4,16-18 Assuming 50% of the subjects complete the lithium treatment and repeat scans and this degree of change, we have a power of between 79% and 90% as this is a paired analysis. Estimated outcome measures will be analyzed for all ROIs and all patients in a linear mixed model with patient as random effect and ROI and remission status as fixed effects. Our previous studies have demonstrated that the standard deviation of BP across patients increases approximately linearly with the mean of the region, and so the BP values are first log-transformed in order to satisfy the assumptions of the modeling (constant variance across regions). For the pre/post imaging of the non-remitters, a linear mixed model will again be used with ROI and condition (before/after) as fixed effects and with two levels of random effects -- a patient effect and a study within patient effect. Many potential covariates will also be measured for each patient and will be included in the model when appropriate. Modeling will be done using R software (www.r-project.org).

F. Funding Status, Details

The study is currently funded through the National Institutes of Health (NIH) through May 31, 2017. Grant Title: Lithium's Molecular Mechanism of Action and the Pathology of Bipolar Disorder

G. Human Subjects Research Protection from Risk

1. Risk to Subjects and 2. Adequacy of Protection Against Risks

Risks associated with participation in this study are related to 1) Drug-free interval; 2) placement of intraarterial catheter; 3) blood sampling; 4) discomfort during scanning (PET and MRI); 5) MRI scan; 6) radiation exposure; 7) toxicology (idiosyncratic reaction to the tracer); 8) genetic testing/confidentiality; 9) pregnancy and 10) risks associated with lithium/lamotrigine use.

Stony Brook University Human Subjects Committee (IRB) PSF 2/23/15

Page 23 of 37

IRB# 2012-1826-F PI: [name] 1. Drug-free interval

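### The 79–90% lithium power appears to leave no allowance for loss after lithium is started: the share assumed to complete equals the share expected to be eligible

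*Protocol*

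**What the plan says.** **Power.** For the lithium effect on 5-HT1A and 5-HTT, the protocol (E. Statistics, Power Analyses) takes a change of 20–25% and the test/retest variability of DASB, described as the higher of the two tracers. It then assumes that "50% of the subjects complete the lithium treatment and repeat scans and this degree of change, we have a power of between 79% and 90" per cent, in a paired analysis. It prints no number of pairs, no SD, no alpha and no sidedness.

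**Eligibility.** Aim 4 (A. Specific Aims) estimates from clinic experience that "50% of the subjects will not be eligible for lithium monotherapy. We propose to treat this group with lamotrigine".

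**Sample.** D.1 Rationale/Overview plans scans in "38 medication free bipolar subjects during a major depressive episode". D.3 Study Sample confirms 38 bipolar, 38 healthy and 10 unipolar subjects.

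**Routes off lithium** (D.5, Treatment Choice):
- Before starting: "If they have not responded to adequate prior lithium treatment while depressed or refuse lithium, they will be given lamotrigine".
- Intolerance: "if patients cannot tolerate treatment, they will be switched to lamotrigine and we will repeat both" tracer scans on lamotrigine.
- Insufficient response: "if patients have not shown at least a 50% improvement in their HDRS score from the baseline interview they will be switched to lamotrigine" (judged at week 6).

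**Tracers.** D.5, PET Studies, adds: "Participants may have only one of these scans, depending on radiotracer availability". The alternate-site section of D.5 scans some patients with a 5-HT1A tracer and describes no DASB scan there.

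**The concern.** The same 50% seems to do two jobs: it is the share that can be given lithium, and it is the share that finishes lithium and is rescanned. Those shares agree only if every patient who starts lithium stays on it, returns for the second session and has the tracer in question both times. The protocol's own treatment and scanning rules make that a best case.

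This is the only power stated for the lithium effect in Aims 2 and 3. If the real number of pairs is lower, a null lithium result would be read against a power the study did not have. The 38 versus 38 baseline comparison does not depend on lithium completion. Nor does the SAP's pre/post sample, which consists of bipolar pairs without restriction to lithium.

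**Working it through.** **Head count.** Inputs are 38 bipolar patients (D.3), 50% not eligible for lithium (Aim 4) and 50% completing lithium with repeat scans (Section E).

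- Expected starters: 38 × (1 − 0.50) = 19
- Assumed completers: 38 × 0.50 = 19
- Implied retention: 19/19 = 100%

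**The stated power.** It cannot be reproduced, because the SD and alpha are not given. I therefore took 79% and 90% as given, assumed 19 pairs and a two-sided 0.05 paired t-test, and solved for the standardized change d in

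power = P(T > t(0.975; n − 1)), with T noncentral t on n − 1 degrees of freedom and noncentrality d√n.

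This gives d = 0.671 for 79% and d = 0.787 for 90%. The implied SDs of change are 20/0.671 = 29.8% and 25/0.787 = 31.8%. They differ. With the single SD that gives 79% at a 20% change, power at a 25% change would be about 93%, not 90%. The stated range therefore does not follow cleanly from the stated range of effects, which is a further reason to treat the figures below as indicative.

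**Power with fewer pairs.** Pairs = 38 × 0.5 × retention, rounded, with d held at the two values above. The retention rates are my assumptions, because the documents give none for lithium starters. The last column is a check: Φ[(1.96 + z)√(n/19) − 1.96], where z is the normal quantile of the stated power.

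| Retention | Pairs | d√n | Power, paired t | Power, normal approximation |
|---|---|---|---|---|
| 100% | 19 | 2.92 to 3.43 | 79–90% (anchored) | 79–90% |
| 90% | 17.1 → 17 | 2.77 to 3.24 | 74–86% | 74–87% |
| 80% | 15.2 → 15 | 2.60 to 3.05 | 68–81% | 69–82% |
| 70% | 13.3 → 13 | 2.42 to 2.84 | 60–74% | 63–77% |

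**Which rules remove a lithium pair.**
- *Intolerance:* yes. The repeat scans are made on lamotrigine. The radiation section (G, item 6) allows up to two injections of each tracer per year, so the second session is used up.
- *One tracer only:* yes, for the tracer not scanned. Section E claims its power for both targets.
- *Refusal:* only if refusers are not already counted within Aim 4's 50%.
- *Less than 50% improvement at 6 weeks:* unclear. The protocol does not say whether a lithium rescan comes before the switch.

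**Other readings of the 50% in Section E.**
- Half of the lithium starters: 9 or 10 pairs, so loss would be covered. At 10 pairs, the SD needed would be about 20–22%.
- Unipolar patients pooled in: 0.50 × 48 = 24 completers from 19 + 10 = 29 starters, or 83% retention. Aims 2 and 3 concern bipolar disorder, however, and Aim 5 keeps the unipolar patients as a separate question.

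**The case against.** The strongest reply is that 19 pairs is an inference. Section E never prints it, and the stated power does not confirm it. An SD of about 30–32% fits 19 pairs and one of about 20–22% fits 10, and the protocol gives no DASB test/retest figure to choose between them. It gives only a coefficient of variation below 10% for CUMI-101 (G, item 7), with DASB described as more variable. This stands, and it is why the wording has to be conditional. The plain reading still favours 19, because Section E and Aim 4 both speak of the subjects without qualification, and Aim 4 means the whole bipolar group.

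The number of starters is also soft. Treatment Choice begins with all patients on lithium and diverts those with failed lithium trials or who refuse, so more than half might start. That is possible, but it departs from Aim 4's own estimate, and the protocol does not reconcile the two.

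Thirdly, the largest loss route may not exist. Treatment Choice places the repeat scans 6–10 weeks after the target dose of either drug before it mentions the 6-week switch, and Section E plans pre/post imaging of non-remitters. Non-responders may therefore supply lithium pairs. This stands too. Intolerance, drop-out and single-tracer scanning remain, at unstated rates.

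A reader might infer that the lithium comparison has been shown to be underpowered, or that its true power is 68%. The documents do not support either. The first would need the number of pairs, the SD and alpha; the second would also need a retention rate.

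**Conclusion.** The point holds in conditional form. If Section E's 50% refers to the 38 bipolar patients, the stated 79–90% is a no-loss figure, because the protocol expects only 19 of them to be eligible for lithium. Its own rules on intolerance and single-tracer scanning make some loss of pairs likely.

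The drop is modest at 90% retention (about 4 to 5 points) and larger at 80% (about 9 to 11 points, with the lower end below 70%). These sizes rest on three assumptions: 79–90% was computed at 19 pairs, the test is a two-sided 0.05 paired t-test, and the retention rates are mine. What the protocol shows is an unstated and apparently missing allowance for loss in Aims 2 and 3. It does not show a proven calculation error or a known shortfall.

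**What to change.** In Section E, Power Analyses:

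1. State the expected number of lithium pairs for each tracer as 38 × eligible share (0.5) × an explicit retention rate. Say whether the present 50% already includes ineligibility.
2. Rerun the power with the sponsor's own test/retest SD and a stated alpha and sidedness, over a range such as 70–90% retention (13–17 pairs).
3. Replace 79–90% with that result. If the existing figure was computed at 19 pairs, it can stay, labelled as the no-loss case.

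The back-solved percentages above should not be copied into the protocol; the sponsor holds the SD and can compute its own.

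The cost is text and one rerun. The downside is that the stated power becomes less favourable. I would not ask for more bipolar patients or for a compulsory lithium rescan before any switch on this ground. The first adds arterial-line PET sessions on the strength of an assumed retention rate. The second takes lamotrigine pairs from Aim 4 and may keep non-responders longer on a drug that is not helping them.

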Official Title: PET and MRI Brain Imaging of Bipolar Disorder

NCT: NCT01880957

Document Date: 12/13/2019

Stony Brook University Human Subjects Committee (IRB) PSF 2/23/15

Page 1 of 37

IRB# 2012-1826-F PI: [name]

COMMITTEES ON RESEARCH INVOLVING HUMAN SUBJECTS Established 1971

Protocol Summary Form

Title: Pathophysiology and Treatment of Bipolar Disorder as Assessed by In Vivo Imaging

Principal Investigator: [name] Co-Investigators: [name], NP

Department: Psychiatry and Behavioral Science

A. Specific Aims

- 1. Quantify serotonin transporter (5-HTT) binding potential (BP) in vivo in bipolar disorder patients (BPD) during a major depressive episode (MDE): Using an older PET ligand for 5-HTT, [11C]McN5652, we find lower 5-HTT BP₁ in medication-free bipolar patients in many brain regions compared to healthy volunteers. [11C]DASB also offers better signal to noise than [11C]McN5652 (Frankle et al., 2004) permitting assay of 5-HTT in the cortex. We hypothesize that untreated bipolar depression will be characterized by lower BP in both subcortical (amygdala, hippocampus, midbrain, thalamus, putamen) and cortical (anterior cingulate and prefrontal cortex) regions as assessed by region of interest and voxel based analyses, reflecting a more widespread abnormality of the serotonergic system than in unipolar depression.
- 2. Assess the effect of lithium treatment of bipolar disorder on 5-HTT. We propose to rescan BPD patients with [11C]DASB 6-10 weeks from the time of therapeutic or highest tolerable dose of lithium monotherapy. We hypothesize that lithium will increase the low 5-HTT BP in BPD patients in the temporal, frontal, and entorhinal cortices towards 'normal' levels. We will determine the relationship between BP change and antidepressant effect.

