PSF 2/23/15 Page 18 of 37

The order of [\(^{11}\)C]CUMI-101 and [\(^{11}\)C]DASB administration may be reversed, or subjects may participate in only one scan (either [\(^{11}\)C]CUMI-101 or [\(^{11}\)C]DASB),.

In cases where the subject has a hemoglobin level less than 12 for males and less than 11 for females, we would forgo blood drawing for the [11C]DASB scan except for one sample to be taken at the 50 minute time point, as outlined in the simultaneous estimation (SIME) approach. Likewise, we would forego blood drawing for the [11C]CUMI-101 scan except for one sample at the 60 minute time point. We have recently confirmed that this provides an excellent estimate of the plasma parameters necessary for quantification and modeling of this radioligand. It involves drawing one 12 cc sample off the arterial line at the 50 min post-radioligand injection time point. Therefore, instead of 120 cc being drawn during the DASB scan, we would reduce the blood drawn to 12 cc.

In the case that the two injections are planned but cannot be done on the same day once the PET procedures have been started, subjects may be asked to return on a separate day in order to complete the scans. If the PET procedure has to be rescheduled and placement of another aline is required, subject consent will be sought.

After the acute treatment period, the patients who are on either lithium or lamotrigine will have a second PET scanning session that is identical to the first: up to 20 mCi or less of [11C]CUMI-101 and up to 20 mCi of [11C]DASB. Healthy volunteers will not have follow up scans.

Alternate Location and Tracer for PET Scans

Due to limited availability of PET scans at the Yale PET center, alternative arrangements will be made for subjects at Stony Brook Medicine. In cases where the subject cannot accommodate a trip to the Yale PET center or the Yale PET center cannot accommodate for enough scans due to decreased scan staff, PET/MRI scans may take place at the Siemens Biograph mMR-System located at the Ambulatory Imaging Center using [18F]MeFWAY. Similar to the [11C]CUMI-101 scans being performed at the Yale PET center, [18F]MeFWAY also has the capability to examine 5-HT_{1A} binding. Only bipolar and unipolar patients will be scanned at Stony Brook, when Yale is unable to accommodate the number of scans necessary. Healthy controls will continue to be scanned at Yale PET Center.

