Official Title: PET and MRI Brain Imaging of Bipolar Disorder

NCT: NCT01880957

Document Date: 11/14/2017

Proposed Statistical Plan for [11C]-DASB (5-HTT) & [11C]-CUMI-101 (5-HT1A) from [name] **Bipolar Study**

Outcomes

DASB: V_T/f_p + bootstrap ROI error

CUMI: BP_F + bootstrap ROI error (BP_{ND}??)

A priori ROIs

DASB: acn, amy, midbrain, gcirc

CUMI: acn, amy, cin, dlPFC, parahippocampal gyrus, hippocampus, raphe

Statistical methods:

Linear mixed models with subject fit as random variable LMM also with DASB & CUMI reference regions and fp

Key outcomes: p-values for main effects/interactions; overall model R² & p-value; standardized & unstandardized β's, 95% CIs, p-values for post-hocs

Covariates

DASB: age

CUMI: age, sex, previous med status (dichotomous – w/n 4 years)

Post-Treatment

Sample: HC, pre BPD, post BPD

Question 1: Do post-treatment BPD levels of DASB or CUMI differ from pre-treatment levels and HCs?

Interactions of interest:

Group (relationship btw brain & Group across all regions) **Group*ROI** (ROI-specific relationship btw brain & Group)

Treatment Effects

Sample: pre/post BPD pairs

Tx response: % change in HDRS-24 (continuous) and remitter/non-remitter (dichotomous)

Question 2: Is the % change in DASB or CUMI associated with the treatment outcome?

Interactions of interest:

AHDRS (relationship btw brain & Tx outcome across all regions) **ΔHDRS*ROI** (ROI-specific relationship btw brain & Tx outcome)

Dichotomous

Interactions of interest:

Remission (relationship btw brain & Tx outcome across all regions)

Predicting Treatment Outcome

Sample: pre BPD with pre HDRS-24 + >7-week HDRS-24

Tx response: % change in HDRS-24 (continuous) and remitter/non-remitter (dichotomous) (responder ??)

Question 3: Do pre DASB or CUMI in any of the *a prioris* predict treatment response? Are the *a prioris* independent predictors of treatment response?

Interactions of interest:

PET roi (pre-treatment PET in ROI predicts treatment response)

Interactions of interest:

PET_roi (any significant ROIs are independent predictors of Tx response (over and above the other ROIs))

Same models fit with dichotomous remission status

Additional question: Do pre DASB & CUMI together predict more of the variance in treatment response than either method alone?

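### The protocol's only before/after model covers non-remitters alone, which does not fit the lithium aims, the power basis or the SAP

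*Protocol*

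**What the plan says.** **Protocol, section E (Statistics, Power Analyses).** Two mixed models on log-transformed BP are described after the lithium power statement.

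- All-patient model: "Estimated outcome measures will be analyzed for all ROIs and all patients in a linear mixed model with patient as random effect", taking "ROI and remission status as fixed effects". It has no before/after term and no drug term.
- Before/after model: "For the pre/post imaging of the non-remitters, a linear mixed model will again be used". Its fixed effects are region and scan condition, and its random effects are at two levels (patient, and study within patient). No other sentence in the protocol names a before/after term.

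The power statement just before these models assumes that half the subjects complete lithium and repeat scanning and that BP changes by 20-25%. It gives 79% to 90% power for a paired analysis.

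**Protocol, section A (Specific Aims).** Aim 2 is not limited by remission: "We hypothesize that lithium will increase the low 5-HTT BP in BPD patients". It adds: "We will determine the relationship between BP change and antidepressant effect". Aim 3 puts the corresponding lithium question for 5-HT1A.

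**Protocol, section D (PET Studies).** Rescanning is not conditional on remission: "the patients who are on either lithium or lamotrigine will have a second PET scanning session".

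**SAP.** The Post-Treatment section compares post-treatment bipolar levels with pre-treatment levels and with healthy controls. The Treatment Effects section relates percentage change in binding to HDRS-24 change and to remission, with "Sample: pre/post BPD pairs". Neither sample is restricted by remission, and neither section names a drug term.

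**The concern.** Remission is known only after treatment. A change model fitted to non-remitters estimates the mean BP change among patients who did not get well. The aims ask about the mean change on lithium. The two coincide only if BP change is unrelated to response, and Aim 2 sets out to study that relation.

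Three things are at stake if the sentence is followed. The paired scans of remitters are collected but do not enter the before/after estimate. The number of pairs drops below the number behind the stated power. The estimate may also be biased for the quantity in Aims 2 and 3. In addition, with two different analysis sets on file and no statement of which document governs, the choice could be made after the data have been seen.

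**Working it through.** **1. Analysis sets side by side**

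| Source | Patients | Before/after term |
|---|---|---|
| Aims 2-3 | Bipolar patients on lithium | implied |
| Power statement, section E | All who complete lithium and rescanning | paired |
| Section E, all-patient model | All patients | none |
| Section E, before/after model | Non-remitters | yes |
| SAP, Post-Treatment and Treatment Effects | Bipolar patients, no remission limit | yes |

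Only the protocol's before/after model selects on outcome.

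**2. Reproducing the stated power**

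Inputs from the protocol: 38 bipolar patients, 50% completing lithium and rescanning, so 0.50 × 38 = 19 pairs; change of 20% or 25%. (Counting the 10 unipolar patients would give 0.50 × 48 = 24.) The SD of the paired change, alpha and sidedness for this calculation are not given. I assume two-sided 0.05 on the raw percentage scale.

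Power is that of a paired t test with noncentrality (change / SD) × √n and n − 1 degrees of freedom.

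- 79% at a 20% change with n = 19 requires SD 29.8%: (20/29.8) × √19 = 2.93. The same SD gives 93% at a 25% change, not 90%.
- 90% at a 25% change requires SD 31.8%: (25/31.8) × √19 = 3.43. That SD gives 74% at a 20% change, not 79%.

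No single SD gives both ends under these assumptions. Using 24 pairs, or log scales, with a two-sided test leaves the same gap: 92-95% at a 25% change. Only a one-sided 5% test on a log-scale increase comes close (91% at a 25% change). The stated range is therefore not reproduced, and below each end is calibrated with its own SD.

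**3. Non-remitters only**

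The remission share is an assumption; pairs = 19 × (1 − share), rounded.

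| Remission share | Pairs | Power, 20% change (SD 29.8%) | Power, 25% change (SD 31.8%) |
|---|---|---|---|
| none excluded | 19 | 79% (calibrated) | 90% (calibrated) |
| 30% | 13 | 60% | 74% |
| 50% | 10 | 47% | 60% |
| 60% | 8 | 38% | 48% |

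For example, at 50% remission the noncentralities are (20/29.8) × √10 = 2.12 and (25/31.8) × √10 = 2.49.

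**4. Possible bias**

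Suppose BP change in the hypothesised direction and clinical improvement are bivariate normal with correlation ρ, and remitters are the best-improving share r. The non-remitter mean is then the true mean minus ρ × SD × φ(k)/(1 − r), where k is the (1 − r) normal quantile. With r = 0.5, φ(0)/0.5 = 0.798, so for ρ = 0.3 the shift is 0.3 × 0.798 × 29.8 = 7.1 points. Apparent mean change when the true mean is 20% (SD 29.8%):

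| ρ (assumed) | r = 30% | r = 50% | r = 60% |
|---|---|---|---|
| 0 | 20.0 | 20.0 | 20.0 |
| 0.2 | 17.0 | 15.2 | 14.2 |
| 0.3 | 15.6 | 12.9 | 11.4 |
| 0.5 | 12.6 | 8.1 | 5.6 |

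With a negative ρ the shift would go the other way.

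**The case against.** The strongest reply is that the SAP already plans the right samples. It compares pre and post levels across bipolar patients and relates binding change to outcome in all pairs. That stands: a reader might infer that the trial has no unrestricted before/after analysis, and the documents do not support that. It does not remove the conflict. The protocol approved on 12/13/2019 still carries the restriction two years after the SAP of 11/14/2017. The funding paragraph describes support through May 2017 as current, so the text may have been carried forward, but that is an inference. The SAP also names no drug term, so as written it pools lithium and lamotrigine pairs.

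A second reply is that remitters are kept in the protocol's all-patient model. This also stands in part. The outcome of that model is not defined. If it is BP change, remitters contribute and change is related to remission. If it is BP at a single scan, they contribute nothing on change. Its single random effect, against two levels in the before/after model, suggests one scan per patient but does not settle the matter. It would be too strong to say that remitters are dropped from every analysis.

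Third, a reader might infer that the lithium effect is certain to be biased towards zero. Aim 2 poses the relation between change and response as a question; if there is none, there is no bias and only precision is lost.

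Fourth, the power figures rest on inputs that the documents do not give, and a single-measure t test stands in for a multi-region mixed model. That is why they are illustrations only.

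**Conclusion.** The point holds as a wrong analysis set in the protocol and a conflict between protocol and SAP. The before/after model is limited to a subgroup defined by post-treatment outcome, while Aims 2 and 3, the rescanning plan and the power statement are not.

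The consequences follow only if the protocol sentence is applied in place of the SAP. In that case, under an assumed 30-50% remission, 19 pairs become 13-10. The nominal 79-90% power becomes about 60-74% at 30% remission and 47-60% at 50%. These figures also assume 19 lithium pairs, two-sided 0.05 and the two back-solved SDs; they are not the trial's actual power. Bias arises only if BP change is related to response, and its size is unknown.

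The count of lithium non-remitters is itself uncertain in either direction. Neither document defines remission. The Treatment Choice section also has patients below 50% HDRS improvement at 6 weeks switched to lamotrigine, while the repeat scan falls 6-10 weeks after the therapeutic or highest tolerable dose is reached. Who is a lithium non-remitter at rescan cannot be read from the text, and these passages must be reconciled with the analysis set.

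**What to change.** In section E of the protocol:

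1. Remove the restriction to non-remitters. Fit the before/after model to all bipolar patients with pre and post scans, keeping ROI and condition as fixed effects and the patient and study-within-patient random effects.
2. Add drug and condition-by-drug, or fit the lithium pairs separately, so that lithium and lamotrigine changes are not pooled. Analyse the unipolar lithium pairs separately (Aim 5).
3. Take the overall before/after change on lithium, from a model without the remission interaction, as the main estimate for Aims 2 and 3. With condition-by-remission in the model under reference coding, the condition coefficient is the change in one remission stratum, not the overall change.
4. Add condition-by-remission as a secondary analysis of the relation to antidepressant effect.
5. Define remission, state the outcome of the all-patient model, and state how patients who switch drug before the second scan are classified, once the 6-week rule and the rescan timing have been reconciled.
6. State the SD, alpha, sidedness and number of pairs behind the 79-90%.

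Make the same drug specification in the SAP and say which document governs. The cost is a short text amendment to both documents, settled before the pre/post data are analysed. It needs no new scans or patients.
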